### 12.3.3. PK Analysis

The concentration-time profiles for kindolor will be evaluated by non-compartmental analysis. Actual sample times will be utilized for calculations. Calculations of parameters and comparisons will be performed with Phoenix WinNonLin 8.2 or higher (Pharsight Corporation, St. Louis, MO). The elimination rate constants ( $\lambda_z$ ) will be estimated from the terminal log-linear decline in plasma concentrations and  $t_{1/2}$  calculated as  $\ln(2)/\lambda_z$ . Area under the plasma concentration curves will be determined until the last time of a quantifiable plasma concentration ( $AUC_t$ ) by the log/linear trapezoidal rule and to infinity ( $AUC_\infty$ ) based on the last plasma concentration ( $C_t$ ) and  $\lambda_z$ . The value of  $T_{max}$  will be the observed time of the highest plasma concentration, and  $C_{max}$  would be the plasma concentration at that time. Mean, SD, geometric mean, median, minimum, and maximum plasma concentrations will be presented for each PK parameter. Concentration time curves by individual subject and by group geometric means  $\pm$  SD will be presented.

### 12.3.4. Baseline Descriptive Statistics

Summaries of the characteristics of the subjects in each of the study groups at baseline will be prepared. A summary will be prepared to show dropouts/retention over time in each group, along with the reason for early termination.

### 12.3.5. Ad Hoc Analyses

*Ad hoc* analyses may also be performed.

### 12.3.6. Interim Analyses and Data Monitoring

An interim analysis of the safety data will be prepared as each cohort completes the study. As 2 placebo subjects will be included in each cohort, the safety data from all placebo subjects will be combined for each interim analysis.

## 12.4. Determination of Sample Size

The cohort size of 6 subjects receiving the active drug is generally accepted for first-in-humans clinical trials that provides a reasonable sample size for PK parameter estimates (Shen-2019). Administration of kindolor tosylate to 6 subjects in each dose group provides a 47%, 62%, 74%, or 82% probability of observing at least 1 occurrence of any AE with a true incidence rate for a given dose group of 10%, 15%, 20%, or 25%, respectively. Furthermore, it will be assumed that pooling the data for the subjects who received placebo (2 from each cohort) provides an adequately sized control group.

### **13. QUALITY CONTROL AND QUALITY ASSURANCE**

This study will be conducted under International Conference on Harmonization (ICH) Good Clinical Practice (GCP) guidelines and all applicable regulatory requirements.

Actions to ensure the accuracy and reliability of data include the selection of qualified investigators and appropriate study centers; the review of protocol procedures with the investigator and study personnel prior to study start; the design of suitable source documents with appropriate instructions for use; the internal audit of source data according to GCP and internal procedures to ensure their accuracy, completeness, and verifiability; as well as the periodic site monitoring by the Sponsor's representatives (clinical monitors of Fast-Track Drugs & Biologics, LLC). Written instructions will be provided for collection, preparation, and shipment of blood samples. Clinical monitors will review source documents and eCRFs for accuracy and completeness during on-site monitoring visits; any discrepancies will be resolved with the investigator, as appropriate.

Significant and/or repeated noncompliance will be investigated, and remedial action instituted when appropriate. Failure to comply with remedial actions may result in study site termination and regulatory authority notification.

#### **13.1. Study Monitoring**

Study monitoring will be the responsibility of designated clinical monitors of Fast-Track. Monitors will assure compliance with the clinical protocol and ICH GCPs, human subject's protection, drug accountability, maintenance of the site regulatory file, and conformance of eCRF data with source documents. Monitoring visits by clinical monitors will be scheduled to take place at the initiation of the study, during the study at appropriate intervals, and after the last subject has completed the study. A report of monitoring observations will be provided to the PI (for corrective actions) and the Sponsor.

#### **13.2. Audits and Inspections**

Authorized representatives of the Sponsor, the FDA, and the IRB may visit the site to perform audits or inspections, including source data verification. The purpose of the audit or inspection is to systematically and independently examine all study related activities and documents to determine whether these activities were conducted, and data were recorded, analyzed, and accurately reported according to the protocol, GCP guidelines, and any applicable regulatory requirements.

The PI will contact the Sponsor's representative and Fast-Track if contacted by a regulatory agency about an inspection.

## **14. ETHICS**

### **14.1. Ethics Review**

The study will be conducted under a protocol reviewed by the site's IRB; the study is to be conducted by scientifically and medically qualified persons; the benefits of the study are in proportion to the risks; the rights and welfare of the subjects will be respected; the physicians conducting the study will ensure that the hazards do not outweigh the potential benefits; the results to be reported will be accurate; subjects will give their informed consent and will be competent to do so and not under duress; and all study staff will comply with the ethical principles in 21 Code of Federal Regulations (CFR) Part 50 and the Belmont Principles.

#### **14.1.1. Review/Approval of Study Protocol**

The study may not begin until the IND has been submitted to the FDA and the 30-day waiting period has expired without notification by FDA to the sponsor of any clinical hold issues. Lohocla Research Corporation will be the study sponsor. The site must obtain written approval from the IRB to conduct the study before study initiation. Lohocla Research Corporation will issue a formal authorization letter for the study to be initiated at the site. Progress reports will be submitted to the IRB by the investigator at the frequency requested by the IRB.

#### **14.1.2. Protocol Modifications**

All necessary protocol changes will be submitted in writing as protocol amendments to the IRB for approval prior to implementation. The sponsor will submit all protocol amendments to the FDA.

#### **14.1.3. Protocol Deviation Reporting Procedures**

All subject-specific deviations from the protocol are to be documented. The PI or designee will be responsible for identifying and reporting all deviations, which are occurrences involving a procedure that did not follow the study protocol. Any protocol deviation that adversely affects the safety or rights of a subject or scientific integrity of the study is considered a major deviation and will be reported immediately to the sponsor and the IRB.

### **14.2. Ethical Conduct of the Study**

This study will be conducted in accordance with all applicable Federal human research protections requirements and the Belmont Principles of respect for persons, beneficence, and justice.

The procedures set out in this study are designed to ensure that the sponsor's representative and all study personnel abide by the principles of the ICH GCP Guideline and the Code of Federal Regulations (CFR). The PI confirms this by signing this study protocol and Form FDA 1572.

#### **14.2.1. Confidentiality**

##### **14.2.1.1. Confidentiality of Data**

Particular attention is drawn to the regulations promulgated by the FDA under the Freedom of Information Act providing, in part, that proprietary information furnished to clinical investigators and IRB will be kept confidential by the FDA only if maintained in confidence by the clinical investigator and IRB.

By signing this protocol, the investigator affirms to the sponsor that information furnished to the investigator by the sponsor will be maintained in confidence and such information will be divulged to the IRB or similar or expert committee; affiliated institution; and employees only under an appropriate understanding of confidentiality with such board or committee, affiliated institution, and employees.

##### **14.2.1.2. Confidentiality of Subject Records**

To maintain subject confidentiality, all laboratory specimens, eCRFs, reports, and other records will be identified by a subject number only. Research and clinical records will be stored in a locked cabinet. Only research staff, the sponsor, and Fast-Track Drugs & Biologics clinical monitors will have access to the records. Subject information will not be released without written permission, except as necessary for monitoring by representatives of the sponsor. By signing the protocol, the investigator agrees that within local regulatory restrictions and ethical considerations, the sponsor or any regulatory agency may consult and/or copy study documents in order to verify eCRF data.

#### **14.2.2. Compensation for Participation**

Subjects will be compensated for travel expenses and for time contributed to this research study in the form of cash or vouchers. Compensation is detailed in the informed consent form.

#### **14.2.3. Written Informed Consent**

The informed consent process and document will be reviewed and approved by the IRB and sponsor's representative prior to initiation of the study. The consent document contains a full explanation of the possible risks, advantages, and alternate treatment options, and availability of treatment in the case of injury, in accordance with 21 CFR Part 50. The consent document indicates that, by signature, the subject permits access to relevant medical records by the sponsor's representative and by representatives of the FDA. The sponsor's representative will submit a copy of the initial IRB- and sponsor's representative-approved consent form to the FDA and will maintain copies of revised consent documents that have been reviewed and approved by the IRB.

A written informed consent document, in compliance with 21 CFR Part 50, 32 CFR Part 219, and the Belmont Principles, and HIPAA Authorization will be signed by the subject before any study-related procedures are initiated for each subject.

All potential subjects for the study will be given a current copy of the informed consent form to read. All aspects of the study and informed consent will be explained in lay language to the subject by either the investigator, or a medically trained designee. Any subject who is unable to

demonstrate understanding of the information contained in the informed consent form will be excluded from study participation.

All study subjects will be given a copy of the signed informed consent form.

#### **14.2.4. Delegation of Responsibilities and Adequate Resources**

The PI should have adequate time to conduct the study properly and should have an adequate number of qualified staff to assist with the conduct of the study.

The term “investigator” used throughout this protocol refers to the PI and/or qualified subinvestigators. The PI may delegate responsibilities to other study site personnel. The PI shall delegate tasks only to individuals qualified by education, training, and experience to perform the delegated tasks. The PI shall have direct oversight of all delegated activities and shall document delegation of responsibilities. The PI is responsible for ensuring all delegated staff has been properly trained on the protocol and their assigned study responsibilities. A delegation log identifying all delegated duties and the individual to whom they have been delegated will be maintained at the study site.

#### **14.2.5. Financial Disclosure**

Clinical investigators are required to provide financial disclosure information for the submission of certification or disclosure statements required under 21 CFR § 54. As defined in 21 CFR § 54.2, a clinical investigator is a listed or identified investigator or subinvestigator who is directly involved in the treatment or evaluation of research subjects. The term also includes the spouse and each dependent child of the investigator. In addition, investigators must promptly update financial disclosure information if any relevant changes occur during the course of the investigation and for 1 year following completion of the study.

## **15. DATA HANDLING AND RECORD KEEPING**

Source documents include but are not limited to original documents, data and records such as hospital/medical records (including electronic health records), clinic charts, laboratory results, data recorded in automated instruments, and pharmacy records, etc. This study will use an electronic data management system (EDMS) (IBM Clinical Development) and eCRFs. Data will be transcribed from source documentation into web-based eCRFs. The transcribed data will be consistent with the source document, or the discrepancies will be explained.

Clinical monitors will review all source records and compare them to the data entered into the eCRF. All entries, corrections, and alterations will be made by the investigator or other authorized study personnel. Any errors identified during monitoring will have a query posted by monitor for site staff to address. The EDMS system maintains a full audit trail of data entry, data corrections, and data queries.

### **15.1. Subject Identification and Confidentiality**

Subjects will be identified on eCRFs by a unique subject number. No personal identifier will be used in any publication or communication used to support this research study. The subject number will be used if it becomes necessary to identify data specific to a single subject. The Sponsor's representative and designated clinical monitors of Fast-Track, the IRB, and the FDA are eligible to review medical and research records related to this study as a part of their responsibility to protect human subjects in clinical research. Personal identifiers will be removed from photocopied or electronic medical and research records.

### **15.2. Inspection of Records**

The sponsor's representative or designee will be allowed to visit the investigation facilities for the purpose of monitoring any aspect of the study. The investigator agrees to allow the monitor to inspect the drug storage area, investigational product stocks, drug accountability records, subject charts, study source documents, and other records relative to study conduct.

Subjects' health information is used to report results of research to the sponsor's representative and Federal regulators and may be reviewed during study audits for compliance with study plans, regulations, and research policies. The consent document indicates that by signature, the subject permits access to relevant medical records by the sponsor's representative and by representatives of the FDA.

Upon a subject's termination from the trial, completed eCRFs will be ready and available for on-site review by the sponsor's representative at scheduled monitoring visits.

### **15.3. Retention of Records**

The investigator is responsible for creating and/or maintaining all study documentation required by Title 21 Code of Federal Regulations (21CFR) Parts 50, 54, 56, and 312, ICH E6 section 8, as well as any other documentation defined in the protocol. The investigator must provide key documents to the Sponsor prior to start of the study. A complete list of required regulatory documents will be provided in the study Manual of Procedures.

Federal and local regulations require that the investigator retain a copy of all regulatory documents and records that support the data for this study for whichever of the following is the longest period of time:

- A period of 2 years following the final date of approval by the FDA or other regulatory agency of the study drug for the purposes that were the subject of the investigation; or
- A period of 5 years following the date on which the results of the investigation were submitted to the FDA or other regulatory agency in support of, or as part of, an application for a research or marketing permit for the study drug for the purposes that were the subject of the investigation.

The Sponsor will notify investigators once one of the above 2 timeframes has been satisfied.

If the investigation does not result in the submission of the data in support of, or as part of, an application for a research or marketing permit, records must be retained for a period of 2 years following notification by the Sponsor that the entire clinical investigation (not merely the investigator's portion) is completed, terminated, or discontinued or 2 years following withdrawal of the Investigational New Drug application/Clinical Trial Authorization or request for marketing approval (New Drug Application/Marketing Authorization Application).

If the investigator retires, relocates, or for other reasons withdraws from the responsibility of keeping the study records, custody must be transferred to a person who will accept the responsibility. The Sponsor must be notified in writing of the name and address of the new custodian. Study records should not be destroyed without consultation with the Sponsor.

## **16. PUBLICATION POLICY**

Review of manuscripts resulting from this study or from data generated during this study must occur according to the Publications Policy in the clinical trial agreement between the PI and Lohocla Research Corporation prior to submission for publication.

## APPENDIX A. STOOL CONSISTENCY QUESTIONNAIRE

1. Frequency of stools per day:	

			
2. Consistency of stools per day:	Using the Bristol Stool Chart - fill in the oval next to the consistency type that best matches your least firm ordinary BM prior to entering the study.  Type 1  Type 2  Type 3  Type 4  Type 5  Type 6  Type 7			
3. Category/ Symptom:	0	1	2	3
a. Urgency of stools	 No urgency	 Somewhat urgent	 Urgent	 Very urgent
b. Abdominal pain or discomfort	 No discomfort	 Mild - moderate discomfort	 Somewhat severe discomfort	 Very severe discomfort
c. Bloating	 No discomfort	 Mild - moderate discomfort	 Somewhat severe discomfort	 Very severe discomfort
d. Interference with performing normal; daily activities	 Not at all	 Some interference	 Much interference	 Incapacitating

BM= bowel movement

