#### **4.9. Benefit/Risk Assessment/Protection Against Risks**

Since this is a Phase 1 study, there are no benefits to the subjects. However, given the current opioid epidemic and the need for safer, more effective non-opioids to treat pain, there are significant benefits to society.

The risks of the study drug are not yet fully known in humans. The nonclinical safety profile of kindolor tosylate has been well characterized through the conduct of genetic toxicology, safety pharmacology, and acute and repeat dose (7-14 days) toxicology studies. Kindolor tosylate is not genotoxic and is not expected to have effects on the central nervous, respiratory, or cardiovascular systems in humans at clinically relevant doses.

The most notable adverse effect associated with kindolor tosylate was the result of local toxicity to the stomach. Repeated oral administration of kindolor tosylate resulted in adverse effects in the stomach in minipigs and to a much lesser extent, in rats. This was characterized initially by soft feces in the minipig. At the end of the dosing period, erosions and ulcerations were observed in the stomachs of rats and minipigs. However, doses that did not cause these effects were identified in both species after repeat dosing over 14-days. Thus, given that single doses, and an enteric coated formulation will be used in this study, the risk of GI toxicity should be low.

Increases in total bilirubin were observed in both rats and minipigs and may be related to the fact that kindolor is a high affinity inhibitor of OATP1B1 and OATP1B3 transporters. There were, however, no correlative histological observations or other clinical chemistry changes, and hepatic effects were reversible upon cessation of dosing. In minipigs only, an increase in renal tubular degeneration/regeneration was noted in both sexes at the two highest doses tested. This renal lesion, commonly observed in nonclinical safety studies, was reversible upon cessation of exposure and was considered non-adverse due to the minimal nature and lack of correlative clinical pathology suggestive of organ dysfunction. Additionally, no alterations in renal parameters (clinical chemistry or histology) were noted in the second minipig study at doses of kindolor tosylate up to 622 mg/kg/day (HED of 444 mg/kg/day).

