**Table 5: Schedule of Visits and Assessments for Each Cohort**

	Outpatient	Inpatient				Outpatient		Early Termination
Activity	Screening	Clinic Intake	Treatment	Follow-up	Clinic Discharge	Follow-up	Telephone Contact a	
Study Day	-30 to -2	-1	1	2	3	7±2		
Informed Consent	X							
Demographics	X							
Medical/Surgical History	X	update						
Physical Examination	X	update			X			X
Height/Weight	X	Weight only				Weight only		Weight only
12-Lead ECG a	X		X	X	X	X		X
Vital Signs b	X	X	X c	X	X	X		X
Serum amylase	X	X			X	X		X
Serum lipase	X	X			X	X		X
Clinical Chemistry d	X	X			X	X		X
Hematology e	X	X			X	X		X
Coagulation f	X	X			X	X		X
Urinalysis g	X	X			X	X		X
Monitor urine output h			X	X	X			
Infectious Diseases i	X							
SARS-CoV-2 Antigen Test j	X							

	Outpatient	Inpatient				Outpatient		Early Termination
Activity	Screening	Clinic Intake	Treatment	Follow-up	Clinic Discharge	Follow-up	Telephone Contact a	
Study Day	-30 to -2	-1	1	2	3	7±2		
Pregnancy Test k	X	X				X		X
Birth control methods	X	update			update		update	
Sperm, ova, donation and breast feeding check		X				X	X	
FOBT	X	X			X	X		
Urine Alcohol & Drug Screen l	X	X						
Prior and Concomitant medications m	X	X	X	X	X	X		X
Eligibility Checklist	X	Final check						
Genetics Tests n		X						
Study Drug Administration			X					
Blood Samples for PK o			X	X	X			
Adverse Events p			X	X	X	X		X
Stool Consistency		X	X	X	X	X		X
Final Subject Disposition						X		X

a A 12-lead resting ECG will be obtained at Screening, Day 1 prior to dosing, at 2, 6, 12, 24, and 48 hours post dose, and early termination.

b Vital signs include sitting (3 minutes) blood pressure, and heart rate, and oral temperature, respiration rate, and pulse oximetry.

c Blood pressure, and heart rate, respiration rate, and pulse oximetry will be taken pre-dose, then at 15, 30, 60 minutes and 2, 4, 6, 12, 24, and 48 hours post dose. Temperature will be taken pre-dose, 24, and 48 hours post dose. All vital signs will be taken at Day 3 before clinic discharge and Day 7.

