#### **11.1.5. Gastrointestinal Adverse Events**

Gastrointestinal (GI) AEs will be assessed as follows:

- Stool Consistency Questionnaire – subject completed questionnaire ([Appendix A](#))
- GI Signs and Symptoms Checklist ([Appendix B](#))
- FOBT
- Open ended questions about AEs that are indicative of gastritis
- Clinical laboratory tests (hematocrit, hemoglobin, blood urea nitrogen (BUN), creatinine, ALT, and AST)
- Endoscopy (if indicated)

A-subject completed Stool Consistency Questionnaire ([Appendix A](#)) that asks 4 questions about GI symptoms will be utilized to assess GI AEs. The responses to the questions are based on a 4-point scale with 0 being no symptom and 3 being a severe symptom. The development of a new symptom or worsening of an existing symptom will be reported as an AE.

In addition, if a subject reports of any of the signs and symptoms of gastritis or potential GI ulcer complications or has a laboratory test result indicative of blood loss as shown in the GI Signs and Symptoms Checklist ([Appendix B](#)), the study gastroenterologist sub-investigator will do a thorough evaluation of the event and perform an endoscopy if it is considered warranted. A signs and symptoms checklist will be reviewed each day starting with Day 1, and then on Days 2, 3, and 7. Presence or absence of each sign or symptom will be recorded and if appropriate, a severity assessment or clinical significance evaluation will be performed.

Clinically significant changes in hematocrit and hemoglobin are defined as decreases of at least 10 percentage points and 2 g/dL, respectively. Clinically significant changes in other clinical laboratory tests will be defined as blood urea nitrogen  $\geq 40$  mg/dL, creatinine  $\geq 1.8$  mg/dL, ALT

and AST  $\geq 3$  times the upper limit of normal. If there is evidence of gastric erosion, ulcer, or bleeding in any subject confirmed by endoscopy or FOBT, the study will be stopped.

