Multiple occurrences of a specific adverse event for a subject are counted once in the frequency for the adverse event. Likewise, multiple occurrences of adverse events within a specific preferred term for a subject are counted once in the frequency for the preferred term.

Programmer's Notes: Order System Organ Class alphabetically and preferred term alphabetically within System Organ Class.

Table 14: Number and Percentage of Subjects with Adverse Events Leading to Withdrawal from the Study

| MedDRA SOC/ Preferred Term | Kindolor 100 mg (N=xx) | Kindolor 300 mg (N=xx) | Kindolor xx mg (N=xx) | Placebo (N=xx) |
|-------------------------------|------------------------------|------------------------------|-----------------------------|-------------------|
| SOC | | | | |
| - Overall - | xx (xx.x%) | xx (xx.x%) | xx (xx.x%) | xx (xx.x%) |
| Preferred term 1 | xx (xx.x%) | xx (xx.x%) | xx (xx.x%) | xx (xx.x%) |
| Preferred term 2 | xx (xx.x%) | xx (xx.x%) | xx (xx.x%) | xx (xx.x%) |

Notes: Percentages are based on the total number of subjects, as given in the column heading.

Multiple occurrences of a specific adverse event for a subject are counted once in the frequency for the adverse event. Likewise, multiple occurrences of adverse events within a specific preferred term for a subject are counted once in the frequency for the preferred term.

Programmer's Notes: Order System Organ Class alphabetically and preferred term alphabetically within System Organ Class.

Table 15: Stool Consistency by Visit

| | | Kindolor 100 mg | Kindolor 300 mg | Kindolor xx mg | Placebo | All subjects |
|---|--|-----------------|-----------------|----------------|--------------|--------------|
| Visit | Characteristic | (N=xx) | (N=xx) | (N=xx) | (N=xx) | (N=xx) |
| Repeat for Treatment, Inpatient Follow-up, Clinic Discharge, Outpatient Follow-up and Early termination | Frequency of Stools per Day | | | | | |
| | Mean (SD) | xx.x (xx.xx) | xx.x (xx.xx) | xx.x (xx.xx) | xx.x (xx.xx) | xx.x (xx.xx) |
| | Median | xx.x | xx.x | xx.x | xx.x | xx.x |
| | Min-Max | (xx-xx) | (xx-xx) | (xx-xx) | (xx-xx) | (xx-xx) |
| | Consistency of Stools per Day | | | | | |
| | Type 1 | xx (xx.x%) | xx (xx.x%) | xx (xx.x%) | xx (xx.x%) | xx (xx.x%) |
| | Type 2 | xx (xx.x%) | xx (xx.x%) | xx (xx.x%) | xx (xx.x%) | xx (xx.x%) |
| | Type 3 | xx (xx.x%) | xx (xx.x%) | xx (xx.x%) | xx (xx.x%) | xx (xx.x%) |
| | Type 4 | xx (xx.x%) | xx (xx.x%) | xx (xx.x%) | xx (xx.x%) | xx (xx.x%) |

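### Item 2 of the Stool Consistency Questionnaire asks about stools before the study, yet it is used and tabulated after dosing, so it cannot validly show a post-dose change in stool type

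*Protocol*

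**What the plan says.** Appendix A of the protocol contains one questionnaire. Item 2 tells the subject to mark the Bristol type that "best matches your least firm ordinary BM prior to entering the study". The other items, such as "Frequency of stools per day" (item 1) and "Urgency of stools" (item 3a), carry no such time reference.

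The schedule of visits has the row "Stool Consistency X X X X X X", which covers Days -1, 1, 2, 3 and 7±2 and early termination. Section 8.8 confirms use on Days 2 and 3 and at the final visit. Section 8.13.1 adds use at discontinuation.

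Section 4.7.4 gives the purpose as assessing change in stool consistency and other GI symptoms, in view of possible gastric toxicity. Section 9.1 lists the questionnaire among the safety endpoints. On the stomach effect in animals, Section 4.9 says: "This was characterized initially by soft feces in the minipig".

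SAP Section 9.2 summarizes the stool items at baseline. The SAP Table 15 shell lists Types 1 to 7 with the instruction "Repeat for Treatment, Inpatient Follow-up, Clinic Discharge, Outpatient Follow-up and Early termination".

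**The concern.** The recall period in item 2 suits Day -1 only. At a later visit, a subject who reads the item and follows it describes a stool from before the study, whatever has happened since the dose. The word *ordinary* makes this worse, because it steers the subject away from an unusually loose stool, which is the event of interest.

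The stake is a misleading safety table. Table 15 would sit beside the baseline table, and similar Bristol distributions could be read as reassurance about consistency when the item never asked about the post-dose period. If some subjects answer literally and others describe their current stool, each cell combines two different quantities, and the table cannot separate them.

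**Working it through.** **Setting the texts side by side**

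| Element | Period it refers to | Source |
|---|---|---|
| Item 2, Bristol type | Before study entry | Appendix A |
| Items 1 and 3a-3d | No pre-study reference | Appendix A |
| When the form is given | Days -1, 1, 2, 3, 7±2, early termination | Schedule of visits; Sections 8.8 and 8.13.1 |
| How item 2 is reported | By visit, from the treatment visit onward | SAP Table 15 |
| Other structured record of stools after dosing | Stool color (melena) and rectal bleeding; no consistency item | Appendix B |
| AE rule tied to the questionnaire | New or worse symptom on a 0-3 scale | Section 11.1.5 |

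Three things follow.

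1. Neither document gives a post-dose version of item 2 or another recall period. That the wording stays the same at each visit is an inference from one form and a repeated schedule. Nothing contradicts it.
2. No other structured item records consistency. The Appendix B checklist has none, and the 0-3 scale in Section 11.1.5 fits the four symptoms of item 3, not the 1-7 Bristol scale.
3. The mismatch is certain for Days 2, 3 and 7±2 and for early termination after dosing. For Day 1 it is open: neither the schedule nor Section 8.6 says whether that form is completed before or after the dose.

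**Illustrating the size**

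The plan's only operating figure is in Section 12.4: the probability of at least one occurrence of an AE among 6 active subjects. The formula is 1 - (1 - p)^6.

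- p = 10%: 1 - 0.90^6 = 46.9% (plan: 47%)
- p = 15%: 1 - 0.85^6 = 62.3% (plan: 62%)
- p = 20%: 1 - 0.80^6 = 73.8% (plan: 74%)
- p = 25%: 1 - 0.75^6 = 82.2% (plan: 82%)

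All four reproduce. Now let p be the true rate of stool softening and s the share of those cases that item 2 records. The documents give no value for s, so it is an assumption and the whole range is shown. The formula becomes 1 - (1 - p × s)^6. For example, with p = 10% and s = 0.5 it is 1 - 0.95^6 = 26.5%.

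| True rate p | s = 0 (wording always followed) | s = 0.5 | s = 1 (every case recorded) |
|---|---|---|---|
| 10% | 0% | 26.5% | 46.9% |
| 15% | 0% | 37.4% | 62.3% |
| 20% | 0% | 46.9% | 73.8% |
| 25% | 0% | 55.1% | 82.2% |

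These figures describe item 2 alone. The sample-size statement itself is not affected.

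**The case against.** The strongest reply is that this is one poorly worded item in a GI assessment with several routes, and that no decision rule depends on it. Much of that stands. The stopping criteria in Section 8.13.2 and the stop in Section 11.1.5 do not refer to Bristol type. AEs are assessed daily and sought with an open-ended question. This limits the importance of the defect but does not make item 2 valid.

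Four stronger readings are tempting, and the documents do not support them.

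- **Post-dose stool change cannot be measured at all.** Frequency, urgency, pain, bloating and interference have no pre-study reference. Under Section 11.1.5, "The development of a new symptom or worsening of an existing symptom will be reported as an AE". Loose stools can also be reported as AEs. What is lost is the structured record of stool type.
- **Change will be zero in all 32 subjects.** This needs every subject to answer literally. Item 2's own label speaks of consistency per day, which points to a current rating, so mixed answers are plausible. In addition, 8 of the 32 (4 cohorts × 2) receive placebo, so at most 24 have a drug effect to miss.
- **The questionnaire was chosen because soft feces came first in animals.** Section 4.7.4 cites potential gastric toxicity in general. Soft feces as the initial sign is stated for the minipig only, after repeated dosing.
- **The response option "Mild - moderate discomfort" undermines the stopping rules.** The investigator grades AE severity under Sections 11.1.3 and 11.1.7, and Section 8.13.2 uses AE and laboratory intensity. Questionnaire scores do not set the grade.

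**Conclusion.** Item 2 is wrong as written for post-dose use. It asks about a period that ended before dosing, and SAP Table 15 would report the answers as post-dose findings. For a listed safety endpoint whose purpose is to assess change in consistency, this should be fixed. It is not critical, because no escalation or stopping rule uses Bristol type and other routes can pick up GI effects.

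The conclusion that item 2 cannot validly show change rests on the single form being used unchanged at each visit. It does not need every subject to answer literally, since mixed answering also makes the table uninterpretable. How much detection is lost does depend on the assumed share s: from nothing lost at s = 1 to all of it at s = 0. The documents do not narrow that range.

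**What to change.** - **Day -1:** keep the present wording of item 2 as the baseline.
- **Post-dose forms:** change item 2 to *your least firm BM since the last questionnaire*, or *since dosing* if the Day 1 form is completed after the dose. Omit *ordinary* and add a *no BM* option.
- **SAP Table 15:** add the shift from the Day -1 type to the worst post-dose type, by treatment group. The present shell has no comparison with baseline.
- **Data already held:** flag item 2 responses collected on the present form, so that similar distributions across visits are not read as absence of effect. SAP Section 3.2 describes several procedures in the past tense, so such data may exist.

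The cost is wording in the form, the eCRF and the SAP shell. Because Appendix A is part of the protocol, Section 14.1.2 requires an amendment with IRB approval before use and submission to the FDA. No procedure or visit is added for subjects, and no dose or stopping rule changes.
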